9.6.3 Analyses of Exploratory Endpoints

- 9.6.3.1 Daily \log_{10} CFU will be plotted against daily TTD and the correlation between these outcomes will be evaluated.
- 9.6.3.2 The ability of the saliva test to accurately characterize acetylator status (fast, intermediate, or slow) as determined by sequencing (gold standard) will be evaluated.
- 9.6.3.3 Prevalence of quinolone **and aminoglycoside resistance** will be reported in a table.

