1.4 Exploratory Objectives

- 1.4.1 Evaluate the correlation between EBA₀₋₇ (TTD) and EBA₀₋₇ (CFU) among participants with smear-positive pulmonary TB.
- 1.4.2 Evaluate the ability of a new PCR method that uses salivary samples to correctly characterize NAT2 genotype compared to standard NAT2 genotyping methods using blood samples and sequencing methodology.
- 1.4.3 Estimate the prevalence of quinolone **and aminoglycoside resistance** among study participants with MDR-TB receiving study treatment.

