In Stage 1, Group 1 participants who do not meet Step 2 entry criteria, all Group 2 participants and all Group 3 participants will be referred to the South African TB Control Programme for treatment. In Stage 2, Group 1 participants who do not meet Step 2 entry criteria, Group 2 participants who do not meet Step 2 entry criteria, and **Group 3 participants who do not meet Step 2 entry criteria** will be referred to the South African TB Control Programme for treatment.

In Step 2, prior to initiation of treatment, sputum will be collected for quantitative culture on solid medium (for **CFU for Groups 1 and 2 only**) and liquid medium (for determination of **TTD for all groups**) and for MIC determination and phenotypic DST. In addition to GenoType MTBDRplus, GenoType MTBDRsI, which identifies additional mutations associated with resistance to fluoroquinolones **and injectable TB medicines**, will be performed on sputum of participants with MDR-TB (but not INH-monoresistant TB) who are enrolled in the study. Sixteen-hour sputum collections will be performed daily during INH treatment, as per standard EBA methodology [42]. Sampling for PK analysis will be performed at steady state on Day 6 (± 1). NAT2 genotyping will be performed on a blood sample to help explain variability in INH PK parameters, and a saliva sample will be collected for evaluation of a new rapid NAT2 genotyping test. Safety and tolerability will be monitored via clinical evaluations throughout the study and through scheduled laboratory evaluations.

To avoid unnecessary delay in initiating TB treatment, screening evaluations for Step 1 and Step 2 may occur on the same day.

To minimize risk to study staff and study participants, participants with MDR-TB will be hospitalized on a different ward from participants with DS-TB or INH-monoresistant TB. Strict infection control practices will be followed, including the wearing of N95 masks where appropriate and hospitalization on wards with negative pressure ventilation. In addition, persons with a previous known exposure to XDR-TB or those who have been treated previously for MDR-TB, and thus have a higher risk of XDR-TB, will not be included in this study.

The study will proceed in two stages, as follows:

Stage 1—Pilot study to ensure feasibility:

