9.2.3 Exploratory Endpoints

9.2.3.1 Daily TTD and \log_{10} CFU per mL sputum between baseline and Day 7. Both TTDs and \log_{10} CFU from the pre-evaluation and entry visits will be averaged and treated as the baseline TTD and \log_{10} CFU.

9.2.3.2 NAT2 genotype results from the new PCR method using saliva sample; NAT2 genotype results from standard methods that use sequencing using whole blood sample. NAT2 acetylator status will be determined based on specimens collected at Step 2 Day 0.

9.2.3.3 MTBDRs/ result (i.e., binary resistance status of quinolone **and aminoglycoside**) based on sputum collected at Step 2 Day 0.

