9.4 Sample Size and Accrual

Primary Objectives:

One of the primary objectives is to estimate the distribution of the EBA_{0-7} (CFU) from each cohort in Group 1 (5, 10, and 15 mg/kg of INH for participants with an *inhA* mutation) and the EBA_{0-7} (CFU) from Group 2 (5 mg/kg of INH for participants without *katG* or *inhA* mutations). **Another primary objective is to estimate the distribution of the EBA_{0-7} (TTP) from each cohort in Group 1, Group 2, and each cohort in Group 3.** The aim is to establish proof-of-concept for the higher doses of INH.

Sample Size:

The planned sample size is 16 participants per treatment **cohort in Group 1 and Group 2**; participants discontinuing before the day 7 sample collection will be replaced. This sample size is similar to that of other recent exploratory EBA studies.

Here is some information about the likely precision of estimates that can be achieved with the planned sample size of 16 participants in this proof-of-concept study. Among participants with DS-TB who were taking 300 mg doses of INH, the estimated mean EBA_{0-5} was $0.21 \log_{10}\text{CFU/mL/day}$ ($n=16$, SE 0.03, between-participant SD 0.12, coefficient of variation [CV] 57%) [41]. We assume the mean EBA_{0-7} (CFU) from Group 1 is approximately half of EBA_{0-7} (CFU) from Group 2. Further assuming constant CV, the table below gives the anticipated precisions (half-widths) of 95% confidence intervals (CIs) around estimates of $\log_{10}\text{CFU/mL/day}$ for any one Group 1 cohort and for the Group 2 cohort, for sample sizes of 10, 16, and 20. Because the MIC distribution may be more variable for Group 1, the table also shows anticipated CI widths for a Group 1 cohort if the CV and SD are larger (114% and 0.120, respectively).

Table 9.4-1: Sample Size per Arm and Expected Half-width of 95% CI for the Hypothesized Mean \log_{10} CFU/mL Decrease per Day with a Range of Estimated CV and SD

Group	Sample Size per Group	Hypothesized Mean \log_{10} CFU/mL/day	CV	SD	Expected Half-width of 95% CI
Any one Group 1 cohort	10	0.105	57%	0.060	0.043
	16	0.105	57%	0.060	0.032
	20	0.105	57%	0.060	0.028
Any one Group 1 cohort	10	0.105	114%	0.120	0.086
	16	0.105	114%	0.120	0.064
	20	0.105	114%	0.120	0.056
Group 2	10	0.210	57%	0.120	0.086
	16	0.210	57%	0.120	0.064
	20	0.210	57%	0.120	0.056

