## 2.6 Exploratory Objectives

1. Evaluate the correlation between EBA0-7 (TTD) and EBA0-7(CFU) among participants with smear-positive pulmonary TB.
2. Evaluate the ability of a new PCR method that uses salivary samples to correctly characterize NAT2 genotype compared to standard NAT2 genotyping methods using blood samples and sequencing methodology.
3. Estimate the prevalence of quinolone, and aminoglycoside resistance among study participants with MDR-TB receiving study treatment.

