### 3.2 Endpoint Definitions

The following is the calculation of log 10 transformed CFU/mL sputum at each time point.

- $\log_{10} \text{CFU/mL} = \log_{10}[(\text{average of CFU/mL}_A \text{ and CFU/mL}_B) \times (\text{dilution factor}) \times 10^{(\text{Dilution})}]$  where the dilution factor is set to 20. CFU/mLA and CFU/mLB are measured from the same sputum sample at a time point.

Example: If CFU/mLA = 150, CFU/mLB = 185, and dilution = 4, then  $\log_{10} \text{CFU/mL} = 7.53$

When multiple TTD results were obtained for a specimen (per Protocol Version 2.0 but not Protocol Version 3.0), the following is the calculation of total TTD.

- The final TTD is the mean of TTDA and TTDB. TTDA and TTDB are measured from the same

sputum sample at a time point. If one of the TTD is missing, the other TTD will be used as the final TTD. In a rare case of observing TTD = 42 days, the sites will determine if the value should be used as is or treated as missing.

The following are definitions from Section 9.2 of the protocol document.

- EBA0-7(CFU)= [baseline log10 CFU/mL sputum (mean of log10 CFU/mL at pre-entry and day 0) – log10 CFU/mL at day 7]/7. For a CFU/ml count of 0, the log10 CFU/mL will be set to 0
- EBA0-7(TTD)= [baseline TTD (mean of TTD at pre-entry and day 0) – TTD at day 7]/7
- EBA0-2(CFU)= [baseline log10 CFU/mL sputum (mean of log10 CFU/mL at pre-entry and day 0) – log10 CFU/mL at day 2]/2. For a CFU/ml count of 0, the log10 CFU/mL will be set to 0
- EBA0-2 (TTD)= [baseline TTD (mean of TTD at pre-entry and day 0) – TTD at day 2]/2.
- EBA2-7(CFU)= (log10 CFU/mL sputum at day 2 – log10 CFU/mL at day 7)/5. For a CFU/ml count of 0, the log10 CFU/mL will be set to 0
- EBA2-7 (TTD)= [TTD at day 2 – TTD at day 7]/5

For Group 3, TTP results from contaminated samples and from TTP from re-culture results after an additional decontamination step will be excluded from analysis.

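### The exploratory objective is the correlation between EBA0-7(TTD) and EBA0-7(CFU), but the stated endpoint and analysis correlate daily levels, which can be strongly related when the two EBAs are not

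*Protocol*

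**What the plan says.** Protocol 1.4.1 states the objective: "Evaluate the correlation between EBA₀₋₇ (TTD) and EBA₀₋₇ (CFU) among participants with smear-positive pulmonary TB". SAP 2.6, item 1, repeats it: "Evaluate the correlation between EBA0-7 (TTD) and EBA0-7(CFU) among participants with smear-positive pulmonary TB".

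Both documents define EBA0-7 as a change per participant, (baseline − Day 7)/7 (Protocol 9.2.1; SAP 3.2). For TTD the SAP takes "baseline TTD (mean of TTD at pre-entry and day 0") as the starting value. A participant's own level therefore cancels.

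The endpoint attached to this objective, Protocol 9.2.3.1, is not EBA0-7. It is daily TTD and daily log10 "CFU per mL sputum between baseline and Day 7". The analysis in Protocol 9.6.3.1 follows that endpoint: daily log10 CFU "will be plotted against daily TTD and the correlation between these outcomes will be evaluated". Neither section says whether days are pooled, taken one at a time, or handled with a repeated-measures method.

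Only two groups can contribute, because Protocol 3.0 plans solid culture for "CFU for Groups 1 and 2 only". Protocol 9.4 gives the numbers for those groups: "The planned sample size is 16 participants per treatment" cohort. SAP 4.3 gives no method for this objective, and SAP 1.1 refers objectives other than primary and secondary ones to a separate SAP for Other Objectives.

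**The concern.** The objective is about change: does a participant whose CFU count falls quickly also show a fast rise in TTD? The analysis is about level: do samples with more colonies turn positive sooner? Two features of daily data make levels correlate whatever the answer to the first question.

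- Participants differ in bacterial burden at the start. A heavily infected participant can have high CFU and short TTD on every day. The Protocol recognises baseline spread elsewhere: 9.6.1.3 adjusts for baseline log10 CFU, and 9.6.2.4 rescales one CFU measure because baseline may differ between groups.
- On effective treatment CFU falls and TTD rises in nearly everyone. That shared trend alone gives a negative correlation across days.

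At stake is a possible misreading. A strong daily correlation could be reported as evidence that the two EBA measures agree when the data say little about that. Group 3 has TTD only, so a reader wanting to interpret its result in CFU terms might look to this analysis.

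**Working it through.** **Plan's own figures.** The documents give no size, precision or power for this correlation. Their SDs for EBA(CFU) can be checked against Table 9.4-1 in Protocol 9.4, using half-width = t(0.975, n−1) × SD/√n. For n = 16, 2.131 × 0.06/4 = 0.032 and 2.131 × 0.12/4 = 0.064, as printed.

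**Inputs from the documents.**
- Mean EBA(CFU): 0.105 in each Group 1 cohort and 0.21 in Group 2. SD: 0.06 to 0.12.
- SD of EBA(TTP): 6. This is stated for Group 3 and borrowed here for Groups 1 and 2.
- Participants with both measures: 4 × 16 = 64 planned; 44 + 16 = 60 enrolled to Steps 1 and 2 (accrual table in the December 2019 clarification memo).

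**Inputs assumed, because the documents do not give them.**
- Baseline log10 CFU SD 0.3 to 1.2, with baseline TTD SD 40 h per log10 of that spread.
- Baseline CFU–TTD correlation 0 to −0.95.
- Noise per sample 0.3 log10 and 15 h (low-noise setting: 0.15 log10 and 8 h).
- Mean TTD rise 8 h/day (16 in Group 2 where cohort means differ).

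**Simulation.** 200 trials per setting, 4 cohorts of 16, baseline (mean of two samples) plus Days 1 to 7. CFU and TTD slopes are drawn independently within cohort, so the true within-cohort EBA correlation is 0.

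| Setting | Pooled daily correlation |
|---|---|
| Equal cohort means, all settings | −0.05 to −0.78 |
| Unequal cohort means, all settings | −0.11 to −0.79 |
| Baseline link −0.8 or stronger, baseline SD ≥ 0.6 | −0.44 to −0.79 |
| Same, low noise, EBA(TTD) SD 6 | −0.56 to −0.81 |
| Same, low noise, EBA(TTD) SD 3 | −0.67 to −0.88 |
| No baseline link | −0.05 to −0.39 |

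In the settings at the base noise:
- the EBA0-7 correlation within cohort stayed between −0.02 and 0.02;
- the EBA0-7 correlation with cohorts pooled and unequal means (0.105 against 0.21) was −0.14 to −0.25;
- the daily correlation within participants was −0.36 to −0.57, from the common trend.

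**Closed-form check.** Put TTD on a scale where its variance components equal those of CFU. Over days 0 to 7 the mean of d² is 17.5 and the variance of d is 5.25. With unrelated slopes, the size of the pooled correlation is

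(ρσ_b² + 5.25m²) / (σ_b² + 17.5σ_E² + 5.25m² + σ_e²).

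Take σ_b = 0.8, σ_E = 0.10, σ_e = 0.3 and m = (3 × 0.105 + 0.21)/4 = 0.131. The trend term is 5.25 × 0.131² = 0.09, and the denominator is 0.64 + 0.175 + 0.09 + 0.09 = 0.995.
- ρ = 1: (0.64 + 0.09)/0.995 = 0.73
- ρ = 0.5: (0.32 + 0.09)/0.995 = 0.41
- ρ = 0: 0.09/0.995 = 0.09

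Here ρ is the size of the baseline CFU–TTD correlation, and it largely decides the answer. The sign in practice is negative.

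**One day at a time.** The trend term drops out but the baseline term stays: ρσ_b²/(σ_b² + d²σ_E² + σ_e²). At Day 7, ρ = 1 gives 0.64/(0.64 + 0.49 + 0.09) = 0.52 and ρ = 0.5 gives 0.32/1.22 = 0.26, again with unrelated slopes.

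**Precision.** The 95% limits at r = 0 by Fisher z are ± tanh(1.96/√(n−3)).
- n = 64: ±0.25. n = 60: ±0.25.
- n = 16 (one cohort): tanh(1.96/√13) = ±0.50.
- 64 × 8 = 512 daily pairs treated as independent: ±0.09, which is falsely narrow.

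**The case against.** **The method may be in another document.** SAP 1.1 sends this objective to the SAP for Other Objectives, which may specify the EBA0-7 correlation. This stands as a caveat. It also means one cannot say that no planned analysis correlates the two EBAs. The conflict between Protocol 1.4.1 and Protocol 9.2.3.1 and 9.6.3.1 remains either way.

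**The text does not say that days are pooled.** Correct: day-by-day or repeated-measures analysis fits the wording too. Neither answers the objective. The day-by-day version keeps the baseline term, and the within-participant version keeps the time trend.

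**The daily correlation need not be high.** This also stands. A reader might infer that it would be strong whatever the EBAs do. The documents do not support that, because values above 0.7 in size need close agreement of CFU and TTD at baseline, which they do not report.

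**Group 3 does not rest on this analysis.** A reader might infer that the Group 3 target of 50% of the Group 2 response depends on TTD standing in for CFU. Protocol 9.2.2.3 sets separate CFU and TTD targets and uses TTD only for Group 3, so TTD is compared with TTD. EBA0-7(TTD) is also a primary endpoint in its own right, and no decision in the documents hangs on the correlation.

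**Timing.** SAP 5 dates the report on Groups 1 and 2 to September 17, 2018, and SAP 4.1 treats changes to outcome measures after post-entry data are seen as post hoc. That calls for a label. It is not a reason to leave the objective unanswered, since the objective already names this correlation.

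**Conclusion.** The mismatch is in the text. The objective names a correlation of two changes, and the endpoint and analysis name daily levels. Carrying out Protocol 9.6.3.1 as written does not answer objective 1.4.1.

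How misleading the result could be is uncertain. With unrelated EBAs the pooled daily correlation ranges from about −0.05 to −0.88. The lower end in size needs no baseline link between CFU and TTD; the upper end needs a strong link, wide baseline spread, low noise and an EBA(TTD) SD of 3 rather than 6. All of these, and the use of the Group 3 SD for Groups 1 and 2, are assumptions.

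The point deserves correction because it is cheap, but its weight is limited: the objective is exploratory and the primary endpoints are unaffected.

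**What to change.** In Protocol 9.2.3.1 and 9.6.3.1, and in the SAP for Other Objectives if it does not already do so:

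1. Make the analysis one pair per participant, EBA0-7(CFU) and EBA0-7(TTD), in Groups 1 and 2.
2. Report the correlation by cohort or adjusted for cohort. Unadjusted pooling brings in the difference in cohort means. Single-cohort estimates will be very imprecise, so a cohort-adjusted estimate is the more useful summary.
3. Give a 95% CI based on the number of participants, not sample-days, and a scatter plot marked by cohort.
4. State the expected sign. EBA(TTD) as defined is negative when TTD rises, so agreement between the measures appears as a negative correlation.
5. Keep the daily plot as descriptive only, and do not offer a within-participant daily correlation as a substitute.

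Both EBAs are already computed as primary endpoints, so the cost is wording, one table and one plot for an exploratory objective. Where Group 1 and 2 data have already been seen, label the analysis post hoc and note that it carries out objective 1.4.1 as stated.

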10.0 PHARMACOLOGY PLAN

10.1 Pharmacology Objectives

See [sections 1.2.2](#) and [1.3.1](#).

10.2 Pharmacology Study Design

10.2.1 Methods and Timing for Assessing, Recording, and Analyzing PK Outcome Measures

Intensive PK sampling will be performed on Day 6 of Step 2 when INH is at steady state, with blood collected pre-dose and at 0.5, 1, 2, 4, 6, 8, 12, and 24 hours post-dose. **PK samples are to be collected at the specified time points within the allowed applicable window periods as follows—pre-dose: 0-10 minutes before dose; 0.5 hours to 8 hours post-dose: ±10 minutes of dosing time; 12 hours and 24 hours post-dose: ±15 minutes of dosing time and prior to next dose.** The INH MIC for *M. tuberculosis* for each individual will be determined and AUC/MIC for each study participant will be estimated, as this is the PD parameter that correlates best with efficacy for this drug against *M. tuberculosis*.

10.2.2 PK Evaluations

PK parameters for INH will be derived from plasma concentration versus time data. Samples will be drawn on a specified study day at optimized sampling times, as per section 10.2.1. The PK parameters to be assessed include:

- AUC_{0-24} – area under the plasma concentration-time curve in one dosing interval over 24 hours;
- C_{max} – maximum observed plasma concentration;
- C_{min} – minimum observed plasma concentration;
- T_{max} – time of maximum observed plasma concentration;
- $T_{1/2}$ – elimination half-life; and
- CL/F – oral clearance.

Individual participant PK parameter values will be derived by noncompartmental methods using a validated PK program. In addition, PK/PD modeling will be performed to evaluate the relationship between drug concentrations and rate or magnitude of bacterial decline. Dates, times, amounts, and fasted/fed status for the last three INH doses will be collected on CRFs. Fasted is defined as nothing by mouth except water and study medications 2 hours pre-dose and 1 hour post-dose. In addition, information that could explain unusual PK values (e.g., vomiting after the dose, not fasting when taken) or reasons for a missed sample (e.g., dropped tube, IV stopped working) are to be reported.

10.2.3 Pharmacogenomics: Host Genetic Analysis

NAT2 genotyping will be performed to determine acetylator status (fast, medium, or slow) and will be used as an explanatory variable in PK analyses.

10.2.4 Pharmacokinetics: Blood Collection and Processing

Blood samples for study drug concentrations will be collected from an indwelling catheter, or, if a catheter cannot be placed successfully, by direct venipuncture. If a catheter is used for blood collection, then prior to blood sampling, the fluid in the catheter will be completely withdrawn at each sampling time and discarded. Each sample will require approximately 4 mL of blood be drawn into one Vacutainer tube.

10.2.5 Sample Processing and Storage

Detailed blood processing, handling, and storage procedures can be found in the A5312 Laboratory Processing Chart (LPC).

Plasma samples will be processed and frozen immediately in an upright position at -70°C or colder, in storage boxes. These samples will be used only for PK studies. They will be stored frozen until study completion. During frozen storage, samples will be labeled with coded sample and volunteer identifiers, and not with name.

10.2.6 Laboratory Performing the Assays

Plasma INH concentrations will be determined by a validated high-performance liquid chromatography procedure performed according to written standard operating procedures. The intraday accuracy and intraday precision will be obtained with quality control samples, which will be analyzed concurrently with each set of volunteer samples. Quality control procedures will be in place to ensure stability of sample materials.

10.3 Primary and Secondary Data, Modeling, and Data Analysis

Refer to [section 10.2.2](#) for definitions of AUC, C_{max} , CL/F, T_{max} , and $T_{1/2}$ for this analysis.

Data will initially be analyzed using noncompartmental methods. The C_{max} , T_{max} , and C_{min} will be determined for each participant by inspection of the serum concentration-versus-time graphs. The AUC from time zero to the time of the last quantifiable concentration (AUC_{0-t}) will be determined by the linear trapezoidal rule.

PK/PD modeling will be performed to evaluate the relationship between drug concentrations and rate or magnitude of bacterial decline. A detailed plan of PK and PK/PD data analysis is included in the Statistical Analysis Plan.

10.4 Anticipated Outcomes

See [Hypothesis 1.1.1](#).

NAT2 acetylator status will explain a large proportion of the variability in INH PK estimates.

11.0 DATA COLLECTION AND MONITORING AND ADVERSE EVENT REPORTING

11.1 Records to Be Kept

CRFs will be provided for each participant. Participants must not be identified by name on any CRFs. Participants will be identified by the patient identification number (PID) and study identification number (SID) provided by the ACTG DMC upon randomization.

11.2 Role of Data Management

11.2.1 Instructions concerning the recording of study data on CRFs will be provided by the ACTG DMC. Each clinical research site is responsible for keying the data in a timely fashion.

11.2.2 It is the responsibility of the ACTG DMC to assure the quality of computerized data for each ACTG study. This role extends from protocol development to generation of the final study databases.

11.3 Clinical Site Monitoring and Record Availability

11.3.1 Site monitors under contract to the NIAID will visit participating clinical research sites to review the individual participant records, including consent forms, CRFs, supporting data, laboratory specimen records, and medical records (physicians' progress notes, nurses' notes, individuals' hospital charts), to ensure protection of study participants, compliance with the protocol, and accuracy and completeness of records. The monitors also will inspect sites' regulatory files to

ensure that regulatory requirements are being followed and sites' pharmacies to review product storage and management.

11.3.2 The site investigator will make study documents (e.g., consent forms, drug distribution forms, CRFs) and pertinent hospital or clinic records readily available for inspection by the local IRB/EC, the site monitors, the NIAID, the OHRP, and **other local, U.S., and international regulatory entities** for confirmation of the study data.

